Recent COVID-19 research has logically focused on the acute diagnosis and treatment of affected patients in order to avoid short-term morbidity and mortality.⁸⁻¹¹ Past research looking at SARS outcomes showed that both the six month exercise capacity and health status of SARS survivors was lower than that of normal controls.¹² Sepsis patients also experience serious disease caused by infection, and long-term reductions in quality of life have been described in survivors of sepsis.¹³ Patients who survive intensive care go on to show deficits in verbal learning and memory,¹⁴ resulting in limitations in returning to work or school.¹⁵ Many SARS survivors developed post-traumatic stress disorder and other debilitating psychological illnesses.¹⁶ Based on the Hong Kong experience with SARS, we are concerned that COVID-19 survivors are at risk for similar challenges in quality of life after discharge from acute care.

The Accident and Emergency Medicine Academic Unit of the Chinese University of Hong Kong based at PWH has worked on multiple studies involving quality of life.^{12,17,18} In particular, we have previously collaborated with [name] and the CUHK Department of Medicine and Therapeutics (M&T) on a quality of life follow-up study on SARS patients.¹² As for studying health-related quality of life, we currently have an ongoing project examining the subject in trauma patients after discharge.¹⁸

Several instruments have been widely used in quality of life research, including the 36-Item Short Form Health Survey (SF-36), the 12-Item Short Form Health Survey (SF-12), the World Health Organization Quality of Life Instruments (WHOQOL-BREF), EuroQoL-5D (EQ-5D-5L) and the Short-Form Six-Dimension (SF-6D). Our team has experience using the SF-36, SF-12v2(HK) and the EQ-5D-5L survey instruments for monitoring quality of life in research subjects in Hong Kong. For example, we found that trauma patients in Hong Kong scored significantly worse on the SF-36 twelve months after injury.¹⁷ We also found the most dramatic improvements happened in the first one to six months post-injury,¹⁹ and that 45% of subjects had achieved an excellent outcome by four years post-injury.²⁰ The SF-12v2(HK) with four week recall is a modified version of the SF-36 to be shorter and quicker to use, while also already translated and validated in Hong Kong.²¹ We aim to combine our experience with conducting quantitative quality of life studies with the CUHK Department of M&T's expertise in coronavirus treatment and follow-up to explore the quality of life of COVID-19 patients in recovery.

The reported mortality rates for COVID-19 has so far been lower than SARS, although the higher absolute numbers of COVID-19 patients mean worldwide deaths are overall much higher. Trauma, sepsis and SARS survivors have all experienced significant long-term morbidity and decreased quality of life as a result of their injuries or infections. A previous study of patients infected with SARS-CoV-1 in 2003 at PWH showed that significant numbers of recovering patients had impaired long-term health status.¹² The question this study hopes to answer is to what degree do COVID-19 patients suffer a similar fate? Has the knowledge gained from the SARS experience led to improved quality of life outcomes compared to SARS survivors? Or do the similarities between the viruses that cause SARS and COVID-19 extend to a reduced quality of life after recovery as well?

Aims

This study aims to determine the quality of life of COVID-19 survivors up to six-months after discharge from hospital or quarantine. We also aim to compare the quality of life of COVID-19 survivors to baseline known Hong Kong quality of life norms.

By identifying overall COVID-19 quality of life as well as specific associations or differences between COVID-19 and baseline local quality of life values, we hope to be able to provide evidence-based conclusions to medical practitioners trying to achieve the best quality of life for patients recovering from COVID-19.

Hypotheses

The null hypothesis is that recovered COVID-19 patients have no difference in quality of life compared to a normal control (baseline Hong Kong quality of life norms).

The alternative hypothesis is that there is a difference in quality of life measures between recovered COVID-19 patients and a normal control.

Plan of Investigation

Subjects

All adult patients aged ≥ 18 years who present to the infectious diseases specialist outpatient follow-up clinic at PWH will be screened for inclusion in this study. The inclusion criteria are age ≥ 18 years, laboratory-confirmed COVID-19 infection with SARS-CoV-2, and patients who agree to follow-up for up to six months following their first interview.

Exclusion criteria:

Patients aged below 18 years will be excluded.

Patients will be excluded if they meet ANY of the following criteria:

Patients or their next of kin are unable to communicate in Chinese or English,

Unwilling or unable to provide written informed consent,

or Patients who will not be available for telephone follow-up at the scheduled times.

We will record all patients who are not enrolled and the reasons for exclusion.

Sample size calculation

As of April 10, 2020, in the NTEC Hospital Authority cluster there have been 89 patients

admitted to PWH (of which 17 patients have already been discharged) and 117 admitted to United Christian Hospital with 42 discharged so far.²² Both PWH and United Christian Hospital's COVID-19 patients will follow-up at the PWH infectious diseases specialist outpatient follow-up clinic. Based on prior studies at PWH with SARS patients, approximately 80% agreed to participate in follow-up studies, so we will likely enroll approximately 200 COVID-19 patients.

Methods

This will be a prospective, observational, multicenter, cohort study. We plan to recruit 100 patients with laboratory confirmed COVID-19 disease who have been discharged from inpatient care or quarantine. Quality of life will be assessed using the SF-12v2(HK) and EQ-5D-5L survey instruments, and their return to work status will be measured up to six months from the date of discharge.

After written consent is obtained, the pre-COVID-19 and baseline information will be collected. Their COVID-19 information will be collected via face-to-face interview or telephone follow-up or by email. 1, 3 and 6-month data post-discharge will be collected via telephone follow-up interview with the patient or e-form completed by the patient.

Quality of life assessment tools

SF-12

The 12-Item Short Form Health Survey is an abbreviated version of the 36-Item Short Form Health Survey. It is a widely used, international, validated survey for investigating health-related quality of life in a variety of both acute and chronic conditions. The survey instrument has eight domains: physical functioning, physical role, bodily pain, general health, vitality, social functioning, emotional role, and mental health. Each domain is measured on a 0-100 scale. A higher score correlates with a higher quality of life. The survey generates a Mental Component Summary (MCS) and a Physical Component Summary (PCS). A Chinese version of the survey, the 12-item Chinese (Hong Kong) Short Form Health Survey (version 2) (SF-12v2 (HK)) has been previously validated and used in Hong Kong.²¹ We will be using the four week recall (standard) version of the SF012v2(HK).

EQ-5D-5L

The EQ-5D-5L is a brief health status measure that comprises of five domains: mobility, self-care, pain, usual activities, and psychological status. EQ-5D-5L has been validated in Hong

Kong, recently for use in patients with chronic obstructive pulmonary disease.²³

Return to work status

Patients' pre-COVID-19 infection work status will be compared to their post-infection status. The type of employment, salary and each patients' subjective work experiences before and after infection will be queried.

Definitions

COVID-19 = Coronavirus Disease 2019, the new disease pandemic caused by the SARS-CoV-2 virus.

CUHK = The Chinese University of Hong Kong

EQ-5D-5L = EuroQol Five Domain survey, one of the two main survey instruments we will use to quantitatively judge quality of life for enrolled study subjects.

NTEC = New Territories East Cluster, a grouping of healthcare facilities in northeast Hong Kong.

PWH = Prince of Wales Hospital, the largest acute care hospital in the Hong Kong Hospital Authority's New Territories East Cluster as well as the major teaching hospital for the Chinese University of Hong Kong's medical school.

SARS = Severe Acute Respiratory Syndrome, the disease associated with the coronavirus epidemic of 2003 (not to be confused with SARS-CoV-2, which is the virus causing COVID-19 disease).

SARS-CoV-2 = Severe Acute Respiratory Syndrome Coronavirus 2, the virus identified as the causative organism of the COVID-19 disease.

SF-12 = The 12-Item Short Form Health Survey, one of the two main survey instruments we will use to quantitatively judge quality of life for enrolled study subjects. We will use the SF-12v2(HK) version of the SF-12, which has been specifically validated for use in Hong Kong.

Study design

Recruitment

All adult COVID-19 patients aged ≥ 18 years who present to the infectious diseases specialist outpatient follow-up clinic at PWH will be screened for inclusion in this study by research assistants involved in this study.

First interview

After consent, the pre-COVID-19 assessments of SF-12v2(HK) and EQ-5D-5L will be obtained

by face-to-face interview or by phone interview by a research assistant or by e-form completed by the patient. The interview process should take no longer than 10 minutes. The questionnaire may be completed by a proxy if the patient is unable to respond to the interviewer. Work status one month prior to COVID-19 diagnosis will be determined at this time as well.

Follow-up interviews

The SF-12v2(HK) and EQ-5D-5L will be obtained by telephone interview from the patient or e-form completed by the patient. The follow-up measures will be performed at 1, 3, and 6-months after date of recovery by a research assistant.

Studies have found differences between quality of life assessments completed by the patient or by proxy. In previous studies, it has been shown that when using EQ-5D-5L as an assessment tool, there is good agreement on the domain of self-care, but only a “fair” agreement on domains such as mobility, pain and anxiety were observed between the patients and caregiver rating.²⁴ However, if all proxy responses were excluded, quality of life for survivors of sepsis with communication problems would not be included, which would be a significant methodological and ethical problem. Thus, in this proposed study, the questionnaire may be completed by a proxy if the patient is unable to respond to the interviewer (e.g. patients with dementia or stroke). A subgroup analysis will be performed accordingly.

Data processing and analysis

Outcomes

Primary outcome

The primary outcome measure will be the health summary scores from SF-12v2(HK) in COVID patients at six-months post-discharge from hospital.

Secondary outcomes

The secondary outcome measures will include the health status measures of the EQ-5D-5L and return to work status in COVID patients at six-months post discharge from hospital.

Other measures

The required clinical data for patient characteristics and data for investigating each patient’s relative illness severity will be collected at the earliest opportunity after subject enrollment. The final COVID-19 diagnosis and any other final diagnoses will be recorded from the patient’s existing clinical notes. The Hospital Authority’s computerized Clinical Management System (the

system used by all hospitals under Hospital Authority for storing and retrieving patients' data) will be reviewed to identify hospital admissions, emergency department reattendance, lengths of stay (intensive care, step-down units or general wards) and mortality.

Statistical analysis

General

Chi-square and Fisher's exact tests will be used for categorical data while t-tests will be used to compare means of continuous variables. A p value <0.05 will be considered statistically significant and all tests will be two-tailed.

Primary analysis

A univariate and multivariate analysis of the data set will be conducted at six months. SF-12v2 dimensions of survivors of COVID-19 will be compared with data from past survivors of SARS infection, sepsis or trauma. We will also compare this data to the general Hong Kong population summary score data. Data from the EQ-5D-5L survey instrument will be compared using the Chi-square or Fisher's exact tests.

Secondary analyses

COVID-19 is still an incompletely understood disease. We will perform secondary analyses on the data to allow us to focus on specific groups and to adjust for variability. We will consider the severity of COVID-19 by examining each patient's clinical record, number of hospital days admitted, number of days spent in the intensive care unit, number and severity of organ(s) dysfunction, co-infections, pathogen(s) identified, pre-COVID-19 health status and pre-existing conditions. It is anticipated that there will be marked changes and differences in health status and functional outcome depending on patient age. Comparisons of quality of life between four time points (pre-sepsis, hospital stay, 3-months and 6-months after discharge) will be assessed using paired t-test or Wilcoxon (W) tests as appropriate.

Multivariate logistic regression analysis

All parameters will be entered into a multiple logistic regression model and used to evaluate associations and account for variation. Multiple logistic regression adjusts for variable interactions and will be used to identify predictors of quality of life in COVID-19 patients during follow-up.

References

1. World Health Organization. *Situation Report-78 HIGHLIGHTS.*; 2020. https://www.who.int/docs/default-source/coronavirus/situation-reports/20200407-sitrep-78-covid-19.pdf?sfvrsn=bc43e1b_2. Accessed April 10, 2020.
2. Centre for Health Protection of the Department of Health of the Hong Kong SAR. *Countries/Areas with Reported Cases of Coronavirus Disease-2019 (COVID-19).*; 2020. https://www.chp.gov.hk/files/pdf/statistics_of_the_cases_novel_coronavirus_infection_en.pdf. Accessed April 10, 2020.
5. Hui DS. Severe acute respiratory syndrome (SARS): Lessons learnt in Hong Kong. *J Thorac Dis.* 2013;5(SUPPL.2). doi:10.3978/j.issn.2072-1439.2013.06.18

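### The plan states two unreconciled enrolment figures, about 200 and 100, and the 200 does not follow from the counts and participation rate given for it

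*Combined protocol and SAP*

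**What the plan says.** The Sample size calculation section (under Plan of Investigation) starts from admission counts at two hospitals, dated 10 April 2020. The total for the first, Prince of Wales Hospital (PWH), is 89. Its discharges and the second hospital's figures are given as: "admitted to PWH (of which 17 patients have already been discharged) and 117 admitted to United Christian Hospital with 42 discharged so far". Both groups are placed in one recruitment pool: "Both PWH and United Christian Hospital's COVID-19 patients will follow-up at the PWH infectious diseases specialist outpatient follow-up clinic". The section then applies a participation rate taken from earlier SARS studies and draws its conclusion: "approximately 80% agreed to participate in follow-up studies, so we will likely enroll approximately 200 COVID-19 patients".

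The Methods section, which follows immediately, gives a different number: "We plan to recruit 100 patients with laboratory confirmed COVID-19 disease who have been discharged from inpatient care or quarantine".

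The Recruitment paragraph under Study design covers all adult COVID-19 patients "who present to the infectious diseases specialist outpatient follow-up clinic at PWH will be screened for inclusion in this study by research assistants". It sets no upper limit. No section calls either number a minimum, a cap, a target, a forecast or the number expected to complete follow-up, and no section links the two.

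**The concern.** There are two separate problems.

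- **Conflict.** Adjacent sections give enrolment as about 200 and as 100. Screening every adult attender fits either number, so the recruitment procedure does not settle which one governs.
- **Arithmetic.** The section presents the 200 as the result of its own counts and its own 80% rate. Those inputs give a clearly smaller number.

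This is the only sample size statement in the document. It gives no effect size, standard deviation or power, so the expected number of patients is the only guide to how precisely the six-month SF-12v2(HK) primary outcome will be estimated. If that number is uncertain by a factor of 2, a reader can judge neither the intended precision nor whether the study reached its planned size.

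**Working it through.** **Inputs, all from Sample size calculation and Methods**

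- Prince of Wales Hospital: 89 admitted, 17 of them discharged
- United Christian Hospital: 117 admitted, 42 of them discharged
- Participation: about 80%
- Stated enrolment: about 200 (Sample size calculation) and 100 (Methods)

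**Step 1: try to reproduce the 200.** Expected enrolment = pool × participation rate.

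- Pool: 89 + 117 = 206
- Yield: 0.80 × 206 = 164.8, about 165
- Ratio of stated to computed: 200 / 164.8 = 1.21, so the stated figure is 21% higher

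The document does not say how loosely to read the 80%. Assuming 75% to 85%:

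- 0.75 × 206 = 154.5
- 0.85 × 206 = 175.1

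The range is about 155 to 175 and does not reach 200.

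**Step 2: try other readings of the same inputs.**

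| Reading | Result |
|---|---|
| 80% of those discharged, 0.80 × (17 + 42) = 0.80 × 59 | 47.2 |
| 80% of those not yet discharged, 0.80 × (206 − 59) = 0.80 × 147 | 117.6 |
| 80% of Prince of Wales admissions, 0.80 × 89 | 71.2 |
| 80% of United Christian admissions, 0.80 × 117 | 93.6 |
| Dividing by the rate, 206 / 0.80 | 257.5 |
| 80% of admissions plus discharges, 0.80 × (206 + 59) | 212 |
| All admissions, rate not applied | 206 |

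None gives 100. Only the last is within 3% of 200, so the rate may have been left out. That is an inference, and the conclusion does not depend on it.

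**Step 3: find what each stated figure would require.**

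- For 200 at 80%: 200 / 0.80 = 250 patients. That is 250 / 206 = 121% of the listed pool, a shortfall of 250 − 206 = 44.
- For 200 from the listed pool: 200 / 206 = 97.1% participation.
- For 100 at 80%: 100 / 0.80 = 125 patients, and 125 / 206 = 61% of the listed pool.
- For 100 from the listed pool: 100 / 206 = 48.5% participation.

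The 147 patients not yet discharged cannot supply the missing 44, because they are already counted in the 206.

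**Step 4: size the consequence.**

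- An enrolment of 164.8 is 164.8 / 100 = 165% of one stated figure and 164.8 / 200 = 82% of the other.
- Confidence interval width for a mean is proportional to 1/√n. The ratio of widths at 100 and 200 is √(200/100) = 1.41 (1.42 with t quantiles), whatever the standard deviation.

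**The case against.** The strongest defence is that the 200 is a forecast and the 100 a target. The count is dated, describes discharges so far, and was taken while cases were still arising. Eligibility depends on attending the clinic, with no cut-off at the count date. The Aims and Methods also cover people leaving quarantine, and the screening text does not restrict patients to the two named hospitals. Later admissions, quarantine discharges or referrals from elsewhere could therefore supply the extra 44. A target below expected availability is also ordinary practice. On this view, 165 is only a snapshot of one date and no better as a forecast.

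Much of this is reasonable. The two numbers can coexist, and the 200 may rest on expected accrual. But the document says neither. The section ties the 200 to the listed counts and the 80% rate and mentions no further source of patients. Even if the 100 is a target, its basis and whether recruitment stops there remain unstated.

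It is also true that the effect is limited. No test in the Statistical analysis section takes the sample size as an input, and there is no stated precision or power goal for a smaller sample to miss. The factor of 1.41 describes the ambiguity, not a failed objective.

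**Conclusion.** The concern holds on both parts. The plan gives two enrolment figures that differ by a factor of 2 with nothing to reconcile them. The 200 is 21% above the 165 that its stated inputs yield, and reaching it at 80% needs 44 patients beyond those listed.

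The 165 rests on the 206 listed admissions and the 80% rate as written. It is generous for that pool, because deaths, patients under 18 and the other exclusions are not deducted. The range of 155 to 175 assumes that approximately 80% means 75% to 85%.

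The harm is to the stated plan and its expected precision, not to the choice of analysis. It should be fixed, and it is not a reason to change the design. The documents do not show which number was intended.

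**What to change.** 1. State one planned number of patients and use it in both Sample size calculation and Methods. The choice of number is the sponsor's.
2. If 100 is the target and 200 a forecast of availability, say so, and say whether recruitment stops at the planned number.
3. Make the forecast follow from its inputs. Either give about 165 before exclusions, labelled as the yield of the listed counts at their date, or keep 200 and state the further accrual assumed. At 80% that means 44 patients beyond the listed 206, with their expected source named.

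The cost is protocol wording only, with no added patients, visits or data. The one downside is that the stated size may look less favourable than about 200.

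### Return to work is compared before and after infection with no recorded reason for not working, so illness cannot be separated from job loss for economic reasons

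*Combined protocol and SAP*

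**What the plan says.** All references are to the combined protocol and SAP.

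- **Design and population.** Methods: "This will be a prospective, observational, multicenter, cohort study". Under Subjects, inclusion requires "laboratory-confirmed COVID-19 infection with SARS-CoV-2", so no uninfected person is enrolled.
- **Work comparison.** Return to work status: "Patients' pre-COVID-19 infection work status will be compared to their post-infection status". The same paragraph says that job type, pay and the patient's own experience of work will be asked about. It names no reason for not working.
- **Work baseline.** First interview: "Work status one month prior to COVID-19 diagnosis will be determined at this time as well".
- **Outcome.** Secondary outcomes lists "return to work status in COVID patients at six-months post discharge from hospital". It does not define return or say which patients form the denominator.
- **Follow-up.** Methods says work status is measured up to six months from discharge. Follow-up interviews names only the two quality-of-life questionnaires at 1, 3 and 6 months.
- **Quality-of-life comparators.** Aims: "We also aim to compare the quality of life of COVID-19 survivors to baseline known Hong Kong quality of life norms". Primary analysis adds: "SF-12v2 dimensions of survivors of COVID-19 will be compared with data from past survivors of SARS infection, sepsis or trauma". Recalled pre-illness scores are also collected, and Secondary analyses plans paired comparisons across time points.
- **Adjustment.** The factors in Secondary analyses are clinical (severity, length of stay, intensive care, organ dysfunction, earlier health), with age also mentioned. None concerns calendar time or economic circumstances.

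**The concern.** A before/after comparison within infected patients takes in everything that changed between the two dates. Infection is one such change, and the pandemic's effect on employers may be another. A patient too ill to work and a patient whose employer closed can both appear as working before and not working after. No uninfected group followed over the same months shows how much of the change would have happened anyway, and no planned question allows the two to be separated within the cohort.

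This matters because the study is meant to inform clinicians caring for recovering patients. Non-return because of persisting ill health calls for a different response from non-return because the job has gone. If the figure is read as a consequence of the illness, it will tend to be too high by an amount nobody can determine afterwards.

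The comparison with existing norms raises a related, weaker question of interpretation. If the norms were collected before the pandemic, a difference from them contains illness plus any change that affected the whole population.

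**Working it through.** **Is there a planned figure to reproduce?** No. The documents give no expected return-to-work rate, no number working before infection and no background rate of job loss. The size can only be shown over stated assumptions.

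**Does any planned comparator remove the background change?**

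| Comparator | Concurrent and uninfected? |
|---|---|
| Own work status one month before diagnosis | No: same patient, earlier date |
| Hong Kong norms | Collection dates not given; already available when the protocol was written (its sources were accessed in April 2020), so probably pre-pandemic |
| Survivors of SARS, sepsis or trauma | No: described as past survivors |
| Recalled pre-illness quality of life | No: same patient, earlier date |
| Severity contrasts within the cohort | Same period, but all infected |

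None does.

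**How far would non-return be inflated?** Let *h* be the true proportion of previously working patients who do not return for health reasons, and *e* the proportion who lose work for employer or economic reasons after the anchor. Assume the two are independent and that nobody is re-employed by six months. Then

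all-cause non-return = 1 − (1 − *h*)(1 − *e*), and the excess over *h* is *e*(1 − *h*).

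| *h* (assumed) | *e* (assumed) | All-cause non-return | Excess (points) | Excess relative to *h* |
|---|---|---|---|---|
| 10% | 5% | 1 − 0.90 × 0.95 = 14.5% | 4.5 | 45% |
| 10% | 10% | 1 − 0.90 × 0.90 = 19% | 9 | 90% |
| 30% | 5% | 1 − 0.70 × 0.95 = 33.5% | 3.5 | 12% |
| 30% | 10% | 1 − 0.70 × 0.90 = 37% | 7 | 23% |

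The relative excess depends heavily on *h*, so the excess in points is the steadier summary: 3.5 to 9 over this grid.

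**Dependence on the assumptions.** If the economic losses fell wholly on patients already off work for health, all-cause non-return would equal *h* and there would be no excess. If the two groups did not overlap at all, it would be *h* + *e*: 15% to 20% for *h* = 10%, and 35% to 40% for *h* = 30%. Re-employment by six months lowers *e*. Job loss before the one-month anchor does not enter *e*.

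**What would a reason item recover?** Under independence a proportion *h* × *e* has both reasons: 0.10 × 0.10 = 1%, or 0.30 × 0.10 = 3%. If reasons are reported correctly, health-related non-return would lie between *h* − *he* and *h*, depending on which reason those patients call the main one. That is 9% to 10%, or 27% to 30%, against all-cause figures of 19% and 37%.

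**The case against.** Several objections are sound and limit the point.

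- **The plan does not state a causal effect.** The hypotheses concern a difference from norms, and the first aim is descriptive. A reader might infer that the plan formally counts pandemic effects as effects of infection. It does not say so. The risk lies in interpretation, although the questions in the background section invite a causal reading.
- **The age of the norms is inferred.** No collection date is given. Probably pre-pandemic is as far as the text allows.
- **A baseline inside the pandemic helps.** Where one month before diagnosis already falls in the pandemic, the baseline absorbs part of the economic shock and the bias shrinks. It would be wrong to count this as a further flaw.
- **The questionnaire is not in the documents.** The question on patients' experience of work might elicit reasons. That stands, but the plan specifies no such item and gives it no place in the outcome.
- **The denominator is unspecified rather than wrong.** A reader might infer from Secondary outcomes that all patients, including those not working before, form the denominator. The phrase may simply name the study population, and the text does not settle it.
- **Severity analyses are already planned.** They are useful, but they compare infected patients with one another and may be confounded by age and earlier health. They do not estimate infection against no infection and so do not close the gap.
- **Every input to the size is assumed.** This is correct, which is why a range over both rates is shown.

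What remains is that the return-to-work result, as specified, cannot distinguish illness from economic job loss.

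**Conclusion.** The point holds in a limited form. Return to work is a within-patient before/after comparison during the pandemic, without a concurrent uninfected group and without a specified reason for not working. Health-related non-return therefore cannot be separated from employer or economic job loss arising after the one-month anchor.

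The bias cannot be computed from the documents. With economic loss of 5% to 10%, health-related non-return of 10% to 30%, independence and no re-employment (all assumed), the excess is 3.5 to 9 percentage points.

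The point concerns a secondary outcome. It does not invalidate the primary outcome or the descriptive aim. For the norm comparison it supports only a sentence of interpretation: the documents do not show that a population-wide fall in quality of life occurred, or how large it would be.

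**What to change.** 1. **Follow-up interviews and Return to work status.** Add one structured item at 1, 3 and 6 months. If the patient is not working or is working less, is the main reason health after COVID-19, an employer or economic reason, or something else?
2. **Secondary outcomes.** Among patients working one month before diagnosis, report all-cause non-return at six months and, beside it, non-return for health reasons. Keep both, so that the self-attributed figure does not stand alone.
3. **Primary analysis (wording only).** State that the comparison with existing Hong Kong norms reflects illness plus any pandemic-period effect, and give the collection dates of the norms.
4. **Secondary analyses (wording only).** Describe the planned severity contrasts as supportive, not as estimates of the effect of infection against no infection.

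The cost is one question in interviews already scheduled and a few sentences of text; no new group is needed. The downside is that a self-reported main reason is imperfect, especially where health and economic reasons coincide. The item needs to be in place during follow-up, because reasons cannot be reliably reconstructed afterwards.
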